The main purpose of this amendment is to implement increased cardiac enzyme monitoring from every six months to every three months based on new cardiac microscopic findings (cardiomyocyte vacuolation) from a wild type RasH2 mouse study with 4-week daily dosing of branaplam at ≥ 10 mg/kg/day. It is not known whether this finding translates to humans. At a dose of 4 mg/kg/day, that did not induce cardiac lesions in the mouse, the area under the plasma (or serum or blood) concentration-time curve for the time period of one week [mass x time / volume] (AUCweek) based exposure multiple for the new findings is 2.2-fold for Type 1 SMA patients (mean of male and female). The observed maximum plasma (or serum or blood) concentration following drug administration [mass / volume] (Cmax)-based exposure multiple is 1.2-fold (mean of male and female).

Following cardiac safety consultation, it was agreed to increase cardiac enzyme monitoring to every three months; and, if any abnormalities are found, an unscheduled ECHO assessment should be performed.

In addition:

• UFB112: The bioanalytical validation of UFB112 failed with initial sample collection and a new analysis method was not completed. To avoid unnecessary blood sample collection and to reduce the total blood volume collected, the determination of UFB112 in blood samples of patients enrolled into Part 3 has been removed from the protocol.

Changes to the protocol

Changes to specific sections of the protocol are shown in the track changes version of the protocol using strike through red font for deletions and red underlined for insertions.

- List of abbreviations has been aligned with amendment 11
- Glossary of terms has been updated to align with Protocol Amendment Template v 4.0
- Protocol Summary has been updated to remove 'Impossibility/inappropriateness of treatment with nusinersen' as an inclusion criteria for Part 2 and to remove caloric intake as an additional assessment
- Section 1.1.1 Relevant data summary: Updated to add new findings from ongoing preclinical studies
- Section 2.2 Secondary objectives: Aligned and corrected Protocol Summary Section with the secondary objectives as follows:
 - 1. Part 1, Part 2, Part 3:
 - a. Removed two endpoints namely 'Discontinuation due to permanent ventilation (defined as more than 21 days for more than 16 hours/day of ventilation) or tracheostomy' and 'Removal of tracheostomy' from the objective 'To evaluate the

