7.4.1 Laboratory evaluations

Clinically relevant deviations of laboratory test results occurring during or at completion of the study must be reported and discussed with Novartis personnel. The results should be evaluated for criteria defining an adverse event and reported as such if the criteria are met. Repeated evaluations are mandatory until normalization of the result(s) or until the change is no longer clinically relevant. In case of doubt, Novartis personnel should again be contacted.

Hematology

Hemoglobin, hematocrit, red blood cell count, white blood cell count with differential and platelet count, platelet volume, reticulocyte count will be measured. Absolute neutrophil count will be calculated.

Clinical chemistry

Following routine clinical chemistry will need to be done according to Assessment Schedule: Sodium, potassium, creatinine, urea, chloride, bicarbonate, high sensitivity CRP, albumin, calcium, alkaline phosphatase, total bilirubin, AST, ALT, TSH (if abnormal, T4 should be assessed), glucose.

In Part 3, routine clinical chemistry will be done at 3-month interval visits. In addition, liver function tests will be done at 1-month interval safety visits; albumin, total protein, ALT, AST, ALP, and total bilirubin. If the total bilirubin concentration is increased above 1.5 times the upper limit of normal, direct and indirect reacting bilirubin should be differentiated.

Additionally, in Part 3, troponin and NTproBNP levels will be assessed at 3-months interval visits

Urine analysis

Urine test by dipstick e.g. Combur9: leucocytes, nitrite, pH, protein, glucose, ketones, urobilinogen, bilirubin, blood/hemoglobin

If the dipstick result is positive for a combination of nitrite, leucocytes and/or blood and protein, it is recommended that the sample is sent for bacteriological culture. Investigators may use clinical judgement for this additional assessment.

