Table 2-16	Worst case direction for each parameter	23
Table 2-17	HINE-2 and the Motor and Speech Domains	28
Table 2-19	Reference ranges for vital sign parameters	35
Table 3-1	Power to detect a difference in CHOP INTEND score between two adjacent dose groups (by one-sided t-test at nominal significance level of 5 percent)	39
Table 5-1	Imputation of start dates (AE, CM)	41
Table 5-2	Imputation of end dates (AE, CM)	41
Table 5-3	Creatinine clearance calculation	43
Table 5-4	Laboratory tests	43
Table 5-5	Prior parameters for bivariate normal distribution of model parameters	46

List of figures

Figure 1-1	Study design for Part 1	8
Figure 1-2	Study design for Part 2	10
Figure 1-3	Study design for Part 3	11

List of abbreviations

AE	Adverse event
ATC	Anatomical Therapeutic Chemical class
AUC	Area Under the Curve
BSA	Body Surface Area
CMAP	Compound Motor Action Potential
CSR	Clinical Study report
CTCAE	Common Terminology Criteria for Adverse Events
DDS	Dose Determining Set
DLT	Dose Limiting Toxicity
DMC	Data Monitoring Committee
eCRF	Electronic Case Report Form
FAS	Full Analysis Set
IA3	Interim Analysis 3
IA4	Interim Analysis 4
MAR	Missing at Random
MedDRA	Medical Dictionary for Drug Regulatory Affairs
Mos.	Months
MTD	Maximum Tolerated Dose
NCV	Nerve Conduction velocity
PD	Pharmacodynamics
PK	Pharmacokinetics
PT	Preferred Term
RAP	Report and Analysis Process
SAE	Serious Adverse Event
SAF	Safety Set
SAP	Statistical Analysis Plan
SD	Standard Deviation
SMA	Spinal muscular Atrophy
SMN2	Survival motor neuron 2
TEAE	Treatment Emergent Adverse Event
TFLs	Tables, Figures, Listings
WHO	World Health Organization

1 Introduction

The Report Analysis Plan (RAP) documents contain detail information to aid the production of Statistics & Programming input into the Clinical Study Report (CSR) for study “**LMI070X2201**”.

The purpose of this Statistical Analysis Plan (SAP) is to describe the implementation of the statistical analysis planned in the protocol, including planned interim analysis (see [Section 2.13](#)) and the full analysis for Parts 1, 2, and 3 after the final database lock.

This document is consistent with the current study protocol amendment version 11, 19-Jul-2021.
Study design

This is an open-label, multi-part, first-in-human proof of concept study in infants with Type 1 spinal muscular atrophy (SMA), to evaluate safety, tolerability, PK, PD and efficacy of oral branaplam. Parts 1, 2, and 3 are intended to be non-confirmatory.

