2.1.1 General definitions

‘**Actual dose**’ will be derived as the current dose for each subject on a daily basis across the entire study; in the case of the day of a dose change, the new dose will be used.

‘**Treatment group**’ in Parts 2 & 3 will refer to the treatment group combination (as mentioned above) for efficacy analyses, and to the actual treatment for safety analyses (see definition below). In Parts 1 & 3, this will be Overall.

‘**Cohort**’ will refer to the initial dose for baseline or demographic characteristics.

The term ‘**Study Day**’ in this document relates to the Analysis Relative Day, Relative Start Day or Relative End Day as applicable. ‘**Study Day**’ is defined relative to the analysis reference date, which is the date of treatment assignment; it is the number of days from the reference date to the analysis date. For all dates on or after the analysis reference date, the study day is the difference to the analysis reference date plus one day (i.e. for date \geq reference date, study day = date - reference date + 1); for any dates prior to the analysis reference date, the study day is

simply the difference to the reference date (i.e. for date < reference date, study day = date - reference date). Thus, the Subject Reference Start Date is designated as Study Day 1, while the date directly prior to the reference date is defined as Study Day -1 (there is no Study Day 0).

'Baseline' is the last non-missing assessment obtained prior to the first administration of study drug. That means that if the measurement at the baseline visit is missing, then the previous measurement preceding baseline will be used as the baseline measurement. For pulse and blood pressure vital sign values, the baseline is the last non-missing value taken prior to the first administration of study drug.

'Treatment phase' includes the time interval on treatment and post-treatment follow-up. Any measurements taken after baseline will be considered as post-baseline measurements.

'Actual treatment' is defined as the treatment group the patient has most exposure to in each Part (for Parts 2 & 3), leading to a treatment group combination; in the case of two treatments having identical exposure, the higher dose will be used. This will be used for safety analyses.

'Calendar age' is defined as the age at the date of evaluation.

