2.8.4 Laboratory data

Data summaries will be provided in SI units. The summary of laboratory evaluations will be presented for three groups of laboratory tests: Hematology, Chemistry and Urinalysis. On presenting summary statistics, laboratory data will be grouped and displayed in an alphabetical order within each of the three groups.

Descriptive summary statistics (mean, median, standard deviation, Min and Max) of the change from baseline in the laboratory result to each study visit-window by treatment group will be presented for continuous variables. Change from baseline will only be summarized for subjects with both baseline and post baseline values and will be calculated as:

$$\text{change from baseline} = \text{post baseline value} - \text{baseline value}$$

In addition, shift tables will be provided for all parameters to compare a subject's baseline laboratory evaluation relative to the post-baseline values. For the shift tables, the normal local

laboratory ranges will be used to evaluate whether a particular laboratory test value was normal, low, or high relative to whether or not the baseline value was normal, low, or high. These summaries will be presented by laboratory test overall in Parts 1 & 3, additionally by actual treatment group in Parts 2 & 3. Shift table will also be provided for urinalysis results to compare baseline to post-baseline extreme values (negative, +, 2+, 3+, or 4+).

Number of subjects with newly occurring liver enzymes abnormalities will be summarized using the respective criteria. Newly occurring liver enzymes abnormalities are defined in [Section 5.3.2](#).

For both shift tables and newly occurring liver enzymes abnormalities, all applicable post-baseline values (including unscheduled or unplanned visits) will be checked against the respective criteria and the rules for handling multiple laboratory assessments within visit windows will not be applied.

For continuous variables databased as <lower limit, these will be imputed as being half of the lower limit.

The following graphs will be generated for liver enzymes:

- Panel plot of individual subjects for alkaline phosphatase, total bilirubin, ALT and AST with dose as background shading – one panel per subject (Parts 1 & 3 and Parts 2 & 3)
- eDISH scatterplot of Total Bilirubin and ALT on log-log axes (Parts 1 & 3); additionally stratified by treatment group (Parts 2 & 3)

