5.3.1 Laboratory test groups and subgroups

On presenting lab results, grouping parameters by family will ease the review. [Table 5-4](#) below shows a possible set of lab parameters and their corresponding classification.

Table 5-4 Laboratory tests

Order	Laboratory Group Subgroups	Tests [SI unit]
1	Hematology	Absolute Basophils [10E9/L] Absolute Eosinophils [10E9/L] Absolute Lymphocytes [10E9/L] Absolute Monocytes [10E9/L] Absolute Neutrophils [10E9/L] Absolute other differentials [10E9/L] Basophils [%] Eosinophils [%] Hematocrit [1] Hemoglobin [g/L] Lymphocytes [%] Mean Platelet Volume [fL] Monocytes [%] Neutrophils [%] Other differentials [%] Platelet count direct [10E9/L] RBC [10E12/L] Reticulocytes [%] WBC (Total) [10E9/L]
2	Chemistry	Albumin [g/L] Alkaline Phosphatase [U/L] ALT [U/L] AST [U/L] Bicarbonate [mmol/L] Bilirubin (direct/conjugated) [umol/L] Bilirubin (indirect/unconjugated) [umol/L] Calcium [mmol/L]

Order	Laboratory Group Subgroups	Tests [SI unit]
		Chloride [mmol/L] Creatinine [umol/L] Free Thyroxine (FT4) [pmol/L] Glucose [mmol/L] hsCRP (high sensitive C-Reactive protein) [mmol/L] Potassium [mmol/L] Sodium [mmol/L] Thyroid hormones T4 [nmol/L] Thyroid stimulating hormone [mU/L] Urea [mmol/L]
3	Urinalysis	Bilirubin Dipstick test Blood Dipstick test Glucose Dipstick test Ketone Dipstick test Leukocytes Dipstick test Nitrite Dipstick test Protein Dipstick test Sediment - Casts Sediment - RBC Sediment - WBC Specific Gravity Urobilinogen pH

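### The visible SAP does not name troponin or NTproBNP, and its pre-first-dose baseline leaves their by-window laboratory summary with no scheduled data for any child

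*SAP*

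**What the plan says.** The rationale for Amendment 11 in the protocol reads: "The main purpose of this amendment is to implement increased cardiac enzyme monitoring from every six months to every three months". The trigger was a heart finding in mice. The SAP introduction states: "This document is consistent with the current study protocol amendment version 11, 19-Jul-2021".

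On sampling, Protocol 7.4.1 says: "Additionally, in Part 3, troponin and NTproBNP levels will be assessed at 3-months interval visits". Table 7-4 schedules both markers from Part 3 Visit 1, and Protocol 3.3 requires them at that visit in all cases. Protocol 4.1.3 admits to Part 3 only children with at least 52 weeks of treatment.

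On analysis, SAP 2.1.1 says that baseline "is the last non-missing assessment obtained prior to the first administration of study drug". It defines no separate baseline for Part 3. For laboratory data, SAP 2.8.4 specifies descriptive statistics of change from baseline in each visit window, and adds: "Change from baseline will only be summarized for subjects with both baseline and post baseline values". It also specifies shift tables from baseline category to post-baseline category. SAP Table 5-4 lists haematology, chemistry and urinalysis tests without either cardiac marker; the text introducing it says that it "shows a possible set of lab parameters and their corresponding classification".

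**The concern.** Safety laboratory parameters are among the primary endpoints in all three parts, and long-term safety is the primary objective of Part 3. Protocol 3.8 names three-monthly troponin and NTproBNP as part of the cardiac risk monitoring and reports three cardiac SUSAR cases. A reader would expect the SAP, which declares itself aligned with version 11, to say how these two markers are summarised. The visible text does not. Liver enzymes, by contrast, receive threshold tables, panel plots, an eDISH plot and a matrix plot.

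Adding the two names to the laboratory table would not be enough. The general laboratory rules assume a value from before treatment, and these markers have none by schedule. A programmer who followed the SAP faithfully would produce a table with no observations for the marker that prompted the current protocol version.

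**Working it through.** The plan gives no figure to reproduce on this point. The check sets the sampling schedule against the SAP rules.

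1. **Parts 1 and 2 schedules.** Protocol Tables 7-1, 7-2 and 7-3 contain neither marker. The routine chemistry panel in Protocol 7.4.1 begins "Sodium, potassium, creatinine, urea, chloride, bicarbonate, high sensitivity CRP, albumin, calcium, alkaline phosphatase, total bilirubin, AST, ALT, TSH" and ends with glucose; neither marker is in it.
2. **First scheduled sample.** Part 3 Visit 1 (Protocol 3.3 and Table 7-4), after at least 52 weeks on drug (Protocol 4.1.3).
3. **Children with a scheduled value before the first dose.** Part 1: 0 of 13 treated. Part 2: 0 of 25 treated. Together 0 of 13 + 25 = 38, or 0%.
4. **Change from baseline (SAP 2.1.1 with 2.8.4).** It needs both a pre-first-dose value and a later value. With no pre-first-dose values, n = 0 in every window, even if both markers are programmed as chemistry parameters.
5. **Raw values.** SAP 2.8.4 specifies no by-window summary of raw laboratory values that could take the place of the empty change summary.
6. **Shift tables (SAP 2.8.4).** Rows are baseline low, normal or high. By schedule, no child has a known row.
7. **Outputs that need no baseline.** SAP 2.8.4 lists all of a child's values for a parameter if any one is out of range. SAP 2.8 analyses clinically significant findings as adverse events. SAP 2.1.1 keeps a category for missing values in other baseline comparisons, with ECGs and vital signs as its examples. The listing covers only children with an out-of-range value, and adverse event capture depends on symptoms, clinical significance or need for therapy (Protocol 9.1.1). None gives a summary by visit or dose group, and a rise within the normal range would not by itself appear in any of them.
8. **With a Part 3 Visit 1 reference.** Change within Part 3 can be calculated for every entrant sampled there and again later. The documents do not give the number of entrants. As an assumed upper bound, 8 Part 1 children ongoing in December 2017 (Amendment 7 rationale) plus 25 Part 2 children gives 33.

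**The case against.** A reader might infer that the markers are in no SAP analysis at all. The documents do not support that. Table 5-4 is expressly illustrative, and the SAP analyses parameters missing from it, such as total bilirubin and estimated creatinine clearance. Protocol 7.4.1 places the markers under clinical chemistry, which SAP 2.8.4 covers, while Table 7-4 places them under other assessments. Inclusion is therefore unspecified, not ruled out. Section 2.12 and parts of Section 4 of the SAP are blacked out, so absence can be asserted only for the visible text. The visible changes listed in Section 4 withdraw no cardiac marker, and Protocol 11.5.2 still promises laboratory summary statistics by visit, part and treatment.

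A reader might also infer that the final analysis could show nothing about these markers. That too goes beyond the text. The out-of-range listing shows the course over time for affected children. Adverse event reporting captures clinically significant elevations. If the missing category in SAP 2.1.1 extends to laboratory data, the shift tables would show children moving from missing to high. The tables of adverse events of special interest rest on an external retrieval sheet that cannot be inspected here.

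Finally, no SAP wording can create pre-treatment samples, and the study calls itself non-confirmatory.

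All of this stands, and it limits the claim. It does not fill the gap: where the SAP does specify a by-window laboratory summary, its own rules leave that summary empty for these two markers, and the remaining outputs show individual abnormalities, not a trend.

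**Conclusion.** The point holds in a bounded form and should be fixed. The visible SAP names neither marker, and under its stated rules the by-window laboratory summary has no scheduled observations for any of the 38 treated children. Nor does any child have a known baseline category for the shift tables. Abnormal individual values could still surface through the listing, a missing-baseline category or adverse event reporting.

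The size describes the protocol schedule, not the database: an unscheduled pre-dose sample cannot be excluded, though nothing in the documents points to one. The conclusion also assumes that the redacted SAP text does not deal with these markers. Cardiac enzyme monitoring was not new in version 11; its frequency was increased. The lack of a pre-treatment value is a limit of the sampling. The part that the SAP can repair is the lack of a reference value and of a summary suited to markers that start in Part 3.

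**What to change.** - State in SAP 2.8.4 and Table 5-4 that troponin and NTproBNP are analysed.
- Define the Part 3 Visit 1 value as an on-treatment reference for these two markers only, and label it as such in every table.
- Summarise raw values and change from that reference in the three-monthly Part 3 windows of Table 2-14, overall for Parts 1 & 3 and by actual treatment group for Parts 2 & 3.
- Count children above the normal limit at any Part 3 visit, and show elevations confirmed on repeat separately. The protocol already asks for a repeat test within one week of a clinically significant increase. Because SAP 2.1.3 keeps only one value per window for summaries, these counts should use all values, as the shift tables already do.

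The cost is SAP wording and one or two tables; no new sampling is needed. The downside is that the reference follows at least 52 weeks of drug, so a rise during that time cannot be detected. The SAP and the study report should say so. Total bilirubin, also missing from Table 5-4, needs no change here because the SAP analyses it elsewhere.

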5.3.2 Newly occurring liver enzymes abnormalities

Below lists the criteria for “events” of newly occurring liver enzymes abnormalities:

- ALT > 3, 5, 10, 20x ULN
- ALT or AST > 3, 5, 8, 10, 20x ULN
- ALT or AST > 3x ULN & TBIL > 1.5x ULN
- ALT or AST > 3x ULN & TBIL > 2x ULN
- ALP > 1.5, 2, 5x ULN
- TBIL > 1, 1.5, 2x ULN
- ALP > 3, 5x ULN & TBL > 2x ULN
- ALT or AST > 3x ULN & TBIL > 2x ULN & ALP \leq 2x ULN
- ALT or AST > 3x ULN & (nausea or vomiting or fatigue or general malaise or abdominal pain or (rash and eosinophilia))

When a criterion contains multiple laboratory parameters (e.g., ALT > 3xULN & TBL > 2xULN), unless otherwise requested by the project clinical team/Brand Safety Leader (BSL), the criterion should be only considered to be met when the elevation in both parameters occurs on the same sample day (as evidenced by the same date that the lab samples were taken).

The “events” are defined in the Novartis safety guideline on hepatotoxicity (Novartis: [[name] 2011](#)), Section: Safety parameters for special liver event analyses.

5.4 Analysis of the primary objective in Part 1

The primary objective of Part 1 is to estimate the Maximum Tolerated Dose (MTD) of branaplam, when administered orally on a once weekly schedule to subjects with Type 1 spinal muscular atrophy. The primary analysis method is an adaptive Bayesian logistic regression model (BLRM) guided by the escalation with overdose control (EWOC) principle (Neuenschwander et al 2008).

5.4.1 Primary endpoint in Part 1

The primary endpoint is the incidence of Dose Limiting Toxicity (DLTs) in the first two weeks after the first dose in Part 1. Estimation of the MTD of LMI070 will be based upon the estimation of the probability of DLT in the first 2 weeks after the first dose in the DDS. This probability is estimated by the model in [Section 5.4.2](#).

For the analysis of the primary variables, the DDS analysis set will be used.

DLTs will be listed and their incidence summarized by primary system organ class, worst grade based on the CTCAE version 4.03, type of adverse event, and by treatment group. The DDS will be used for these summaries.

5.4.2 Statistical hypothesis, model, and method of analysis in Part 1

The dose-toxicity (DLT) relationship in each dose escalation will be described by the following logistic regression model:

$$\text{logit}(\pi_{(d)}) = \log(\alpha) + \beta \log(d/d^*), \alpha > 0, \beta > 0$$

where, $\text{logit}(\pi_{(d)}) = \ln(\pi_{(d)} / (1 - \pi_{(d)}))$, and $\pi_{(d)}$ is the probability of a DLT at dose d , where d represents the total weekly dose in Part I. Doses are rescaled as d/d^* with reference dose of $d^* = 40 \text{ mg/m}^2$ of branaplam. As a consequence, α is equal to the odds of toxicity at d^* . Note that for a dose equal to zero, the probability of toxicity is zero.

The following sub-sections provide details for dose recommendation and prior distribution for the model parameters.

Dose recommendation

After each cohort is completed the posterior distributions for the probabilities of DLT at different dose levels will be obtained. The results of this analysis will be summarized in terms of the estimated probabilities that the true rate of DLT at each dose-level will lie within each of the following intervals:

- [0, 10%) under-dosing.
- [10%, 25%) targeted toxicity.
- [25%, 100%) excessive toxicity.

Following the principle of escalation with overdose control (EWOC), after each cohort of subjects the recommended dose will be the one with the highest posterior probability of the DLT rate falling in the target interval [10%, 25%) among the doses fulfilling escalation with overdose control (EWOC), i.e. it is unlikely (< 25% posterior probability) that the DLT rate at

the dose falls in the excessive toxicity interval i.e. $P(DLT)$ is 0.25 or higher. In addition, the maximum dose escalation is limited to 100% of the previous dose.

Note that the dose that maximizes the posterior probability of targeted toxicity is the best estimate of the MTD, but it may not be an admissible dose according to the overdose criterion if the amount of data is insufficient. If vague prior information is used for the probabilities of DLT, in the early stages of the study this escalation procedure will reflect a cautious strategy. The dose recommended by the adaptive Bayesian logistic model may be regarded as guidance and information to be integrated with a clinical assessment of the toxicity profiles observed at the time of the analysis in determining the next dose level to be investigated.

Prior specification

A vague bivariate normal prior for the model parameters ($\log(\alpha)$, $\log(\beta)$) is derived by assuming that the median DLT rate at reference dose $d^*=40 \text{ mg/m}^2$ equals the targeted toxicity 0.25, and that for the remaining doses, median DLT rates a priori are linear in logit scale as a function of log-dose.

The information to derive the prior distribution of model parameters is provided in [Table 5-5](#).

Table 5-5 Prior parameters for bivariate normal distribution of model parameters

Parameters	Means	Standard deviations	Correlation
$\log(\alpha)$, $\log(\beta)$	(-1.099, 0)	(3.2, 1)	0

All information obtained on adverse events will be displayed by initial and administered dose and subject.

5.4.3 Interim analysis in Part 1

After each cohort of subjects finish first dosing and contribute safety data at week 2, an interim analysis (without requirement for database lock) will be conducted for dose escalation decisions. The analysis will be comprised of fitting a Bayesian logistic regression model (BLRM) based on the dose limiting toxicity (DLT) information. From this model, the posterior probability of DLT rate at different dose levels will be estimated and a dose will be recommended to guide dose selection for the next cohort or declaration of MTD. In general, the next dose will have the highest chance that the DLT rate will fall in the target interval [10%, 25%) and will always satisfy the escalation with overdose control (EWOC) principle that the posterior probability of DLT rate falling in overdosing interval (>25%) is below 25%. In all cases, the dose for the next cohort will not exceed a 100% increase from the previous dose. Final dose escalation decisions will be made by Investigators and Novartis study personnel. Decision will be based on a synthesis of all relevant data available from all dose levels evaluated in the ongoing study, including safety information, DLTs, and available PK data from evaluable subjects. Dose escalation will continue until identification of the MTD.

An interim analysis is planned after MTD determination in Part 1 to evaluate PD effects of the treatment and assist with decision making for Part 2. Data on muscle thickness, ratio of muscle thickness to subcutaneous tissue thickness and muscle echo intensity, growth measurements, respiratory function assessments and CHOP INTEND infant motor scale will be summarized at different time points and compared to baseline.

The Interim Analysis Team may communicate interim results (e.g. evaluation of PoC criteria or information needed for planning/modifying another study) to relevant Novartis teams for information, consulting and/or decision purposes.

6 References

Garwood F. (1936) Fiducial Limits for the Poisson Distribution. *Biometrika* 28, 437-442.

